In a single-dose intravenous and subcutaneous pharmacokinetic study in cynomolgus monkeys, doses of 0.3 mg/kg IV and 0.06, 0.3, and 1.5 mg/kg SC were administered. At the 1.5 mg/kg dose, one animal was euthanized due to moribund condition, and multi-organ thrombosis was considered the likely cause. The moribund condition of this animal was considered possibly related to the test article. In a repeat-dose toxicity study in healthy cynomolgus monkeys, subcutaneous injections were administered at 0.1, 0.3, and 1.5 mg/kg every 2 weeks for 4 weeks, for a total of 3 doses. In the 1.5 mg/kg dose group, two animals developed tail ulceration prior to dosing, and the pharmacological effect of the test article exacerbated distal tissue abnormalities post-dosing, ultimately resulting in moribund condition/euthanasia. In the 0.1 and 0.3 mg/kg groups, apart from tissue injury caused by pharmacological exacerbation of ulceration/scabbing, no other significant abnormalities were observed. Therefore, the NOAEL was established at 0.3 mg/kg. Referring to relevant guidelines and guidance documents, calculated for an adult body weight of 60 kg, the HED is 0.097 mg/kg (0.3/3.1). Given that the preclinical toxicity studies were conducted in healthy cynomolgus monkeys, while the clinical trial will be conducted in a patient population, a safety factor of 5 was considered, resulting in an MRSD of 0.019 mg/kg.

In a 14-week repeat subcutaneous and intravenous toxicity study in cynomolgus monkeys (with an 8-week recovery period), SR604 was administered subcutaneously at 0.03, 0.1, and 0.3 mg/kg every 2 weeks for 14 weeks, for a total of 8 doses, followed by an 8-week recovery period. No mortality or moribund condition was observed in animals of any dose group. Clinical observations included tail ulceration/scabbing, with distal tail necrosis due to pharmacological exacerbation of injury. Transient slight elevation of IL-6 was observed in individual animals. At the end of the 8-week recovery period, the above changes were reversible. No other systemic toxicological changes were observed. No significant abnormalities were observed in safety pharmacology parameters of the central nervous system, cardiovascular system, respiratory system, or other organs and tissues (including male and female reproductive organs) in any dose group. SR604 was

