product-related adverse reactions, 2 additional subjects will be enrolled in Cohort 1. If the first subject or any subject in Cohort 1 experiences Grade 3 or higher investigational product-related adverse reactions within 29 days post-dose, or if ≥ 2 of the 3 subjects in Cohort 1 experience Grade 2 or higher investigational product-related adverse reactions within 29 days post-dose, a Scientific Review Committee (SRC) composed of the principal investigator, sponsor, and other professionals will comprehensively evaluate whether to continue the trial.

After completion of Cohort 1 (0.025 mg/kg, starting dose), all subsequent dose cohorts will transition to a "3+3" dose escalation model. The safety monitoring timepoint (Dn) for dose escalation in subsequent cohorts may be adjusted as necessary based on previously obtained study results.

For each dose cohort, after completing the Day Dn safety visit for 3 evaluable subjects, the SRC will review and assess the safety data. If the dose escalation stopping criteria are not met, the current dose cohort will be concluded, and escalation to the next dose cohort will proceed. If ≥ 1 of the initial 3 evaluable subjects in a dose cohort experiences Grade 3 or higher investigational product-related adverse reactions within Dn days post-dose, or ≥ 2 subjects experience Grade 2 or higher investigational product-related adverse reactions within Dn days post-dose, 3 additional evaluable subjects will be enrolled. If ≥ 2 of the 6 evaluable subjects experience Grade 3 or higher investigational product-related adverse reactions within Dn days post-dose, or ≥ 4 subjects experience Grade 2 or higher investigational product-related adverse reactions within Dn days post-dose, that dose group will be terminated or dose reduction will be pursued for further exploration. Otherwise, the current dose cohort will be concluded, and escalation to the next dose cohort will proceed.

If one investigational product-related thromboembolic event of Grade 2 or higher occurs in any dose cohort, the SRC will conduct risk analysis and evaluation before determining whether to enroll new subjects and continue the trial.

All adverse events and laboratory abnormalities will be assessed for safety outcomes according to the baseline criteria of the NCI-CTCAE Version 5.0.

Investigational Medicinal Product

Name: SR604 Injection

Strength: 30 mg (1 mL)/vial

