During the PK/PD blood collection period for subjects in Cohort 3 and subsequent dose cohorts, vital signs will be monitored at the following timepoints: within 1 h predose, and at 2 h (± 15 min), 8 h (± 15 min), D2, D3, D5, D6, D8, D11, D15, D22, D29, D36, D43, D57, D71, D85/post-early withdrawal postdose. Coagulation function [PT results will also be used for PD parameter analysis] will be monitored at: within 1 h predose, and at 2 h (± 5 min), 8 h (± 10 min), D2, D5, D8, D15, D29, D43, D57, D85/post-early withdrawal postdose. Electrocardiograms will be monitored at: within 2 h predose, and at 8 h (± 1 h), D2, D5, D8, D15, D29, D43, D57, D85/post-early withdrawal postdose. Other safety and tolerability parameters will also be observed.

At 672 h (D29) postdose, the investigator will perform safety assessments including vital signs, physical examination, adverse event assessment, laboratory tests (complete blood count, urinalysis, and blood biochemistry), coagulation function, FDP, 12-lead ECG, anti-SR604 antibodies (ADA), and neutralizing antibodies. Combined with safety parameter monitoring results during the PK/PD blood collection period, the SRC will conduct a comprehensive safety review of the dose cohort (whether dose escalation stopping criteria have been met) and assess the feasibility of proceeding to the next dose cohort (or dose adjustment). After completing the 29-day follow-up, subjects in Cohort 1 will continue follow-up per the amended protocol (Ver 1.1) to Day 57 post-dose for PK/PD blood collection and corresponding assessments. Subjects in Cohort 2, Cohort 3, and subsequent dose cohorts will continue follow-up to D85 for PK/PD blood collection and corresponding assessments.

If a subject withdraws or exits the trial early at any time during the trial, safety assessments including body weight, vital signs, physical examination, laboratory tests (including complete blood count, urinalysis, and blood biochemistry), coagulation function, FDP, 12-lead ECG, anti-SR604 antibodies (ADA), and neutralizing antibodies must be performed. Bleeding events and their treatment, adverse events, and concomitant medications/treatments will be recorded. If safety evaluation parameters are abnormal, follow-up must continue until values return to normal, are deemed not clinically significant, are stable, or return to baseline.

Part B: Consists of a screening period, treatment period, extension treatment period, and follow-up period.

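### Part A: the Grade ≥3 expansion trigger has no upper limit, so three more patients are enrolled after 2 or 3 of 3 reactions have already settled the outcome (relevant if 0.8 mg/kg is still to be dosed)

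*Protocol*

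**What the plan says.** The rules are in the protocol section Dose Escalation Principles (Part A). For every cohort after the first, the SRC reviews safety once three evaluable subjects have reached the safety visit. The expansion sentence begins "If ≥ 1 of the initial 3 evaluable subjects in a dose cohort experiences Grade 3 or higher investigational product-related adverse reactions". A parallel leg applies when at least two of the three have related reactions of Grade 2 or higher. In either case, "3 additional evaluable subjects will be enrolled". The ending rule is written for the enlarged cohort: "If ≥ 2 of the 6 evaluable subjects experience Grade 3 or higher investigational product-related adverse reactions within Dn days post-dose", or at least four have Grade 2 or higher, the dose group is terminated or the dose is reduced. No termination criterion is given for a cohort of three.

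Two neighbouring rules matter:

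- **Cohort 1:** "If the first subject or any subject in Cohort 1 experiences Grade 3 or higher investigational product-related adverse reactions within 29 days post-dose", the SRC decides whether the trial continues.
- **All cohorts:** "If one investigational product-related thromboembolic event of Grade 2 or higher occurs in any dose cohort", the SRC evaluates the risk before any new subject is enrolled.

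The status of Part A is unclear. Trial Design and Dose Escalation Principles list six cohorts up to 0.8 mg/kg. Dose Selection and Rationale calls the Phase I escalation completed and reports 13 patients, from 0.025 to 0.4 mg/kg, with no adverse drug reactions in 29 days. It gives no result for 0.8 mg/kg and does not say that the cohort was dropped.

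**The concern.** In a 3+3 scheme the second group of three is there to resolve doubt. One reaction in three leaves doubt; two or three in three do not, because the protocol's own limit of two has been reached. Dosing three more patients at that level cannot change whether the limit is met. It can only inform the choice between ending the dose group and reducing the dose.

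Among the reported doses the rule was never triggered, so it could matter only at 0.8 mg/kg. With the monkey-to-human factor of 3.1 used in Dose Selection and Rationale, the 1.5 mg/kg monkey dose corresponds to about 0.48 mg/kg in humans, which is below 0.8 mg/kg. At 1.5 mg/kg one monkey became moribund and "multi-organ thrombosis was considered the likely cause", an event of the kind the thromboembolic clause covers. In the repeat-dose study at the same dose, "two animals developed tail ulceration prior to dosing, and the pharmacological effect of the test article exacerbated distal tissue abnormalities post-dosing", ending in moribund condition or euthanasia. The protocol does not describe those two cases as thromboembolic, so the clause might not catch a similar reaction in a patient.

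**Working it through.** **1. The plan's own figure.** Sample Size gives about 16–33 evaluable subjects for Part A, with 1–3 in Cohort 1 and 3–6 in each of five later cohorts. Minimum: 1 + 5 × 3 = 16. Maximum: 3 + 5 × 6 = 33. Both agree, so the range counts the 0.8 mg/kg cohort. The 13 reported patients are 1 + 4 × 3.

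**2. Enumeration of the Grade ≥3 leg.** This step needs no assumed rate.

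| Affected among first 3 | Expand as written? | Possible total of 6 | Limit of 2 certain? |
|---|---|---|---|
| 0 | no (on this leg) | – | no |
| 1 | yes | 1–4 | no |
| 2 | yes | 2–5 | yes |
| 3 | yes | 3–6 | yes |

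The Grade ≥2 leg does not have this problem: even 3 of 3 gives 3–6 of 6, which does not force 4.

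**3. How often it would happen.** The protocol gives no expected toxicity rate. Let p be an assumed related Grade ≥3 rate, s an assumed share of those reactions that are thromboembolic, and q = p(1 − s). The chance that at least two of three have Grade ≥3 reactions and none is thromboembolic is 3q²(1 − p) + q³. The expected number of extra exposures is three times that. The value p = 33% is the rule's own fraction, 2 of 6.

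Example with p = 0.20, s = 0: 3 × 0.04 × 0.80 + 0.008 = 0.104, and 3 × 0.104 = 0.31 patients.

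| s | p = 5% | p = 10% | p = 20% | p = 33% |
|---|---|---|---|---|
| 0 (upper bound) | 0.7% | 2.8% | 10.4% | 25.5% |
| 25% | 0.4% | 1.6% | 5.7% | 13.8% |
| 50% | 0.2% | 0.7% | 2.5% | 5.9% |
| 75% | 0.05% | 0.2% | 0.6% | 1.4% |

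Expected extra exposures at s = 0 are 0.02, 0.08, 0.31 and 0.76 patients. At s = 50% they are 0.005, 0.02, 0.075 and 0.18. Grade 2 thromboembolic events would lower these further.

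**4. Effect of a cap on the decision.** On the Grade ≥3 leg, the probability of termination under both wordings is P(≥2 of 3) + 3p(1 − p)² × [1 − (1 − p)³]. At p = 0.20: 0.104 + 0.384 × 0.488 = 0.291. Expected cohort size is 3 + 3[1 − (1 − p)³] as written and 3 + 3 × 3p(1 − p)² when capped. SRC discretion and the thromboembolic hold are left out.

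| | p = 5% | p = 10% | p = 20% | p = 33% |
|---|---|---|---|---|
| P(terminate or reduce), both wordings | 2.7% | 9.4% | 29.1% | 56.6% |
| Expected size, as written | 3.43 | 3.81 | 4.46 | 5.10 |
| Expected size, capped | 3.41 | 3.73 | 4.15 | 4.33 |

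With the Grade ≥2 leg added and 10% of patients having Grade 2 only, full enumeration gives 3.0%, 9.9%, 30.0% and 57.7%, again the same under both wordings.

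**5. What the existing data exclude.** With 0 related reactions in 13 patients, the pooled one-sided 95% upper bound is 1 − 0.05^(1/13) = 20.6%. It refers to doses up to 0.4 mg/kg and sets no limit at 0.8 mg/kg.

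**6. Dose comparison.** 1.5 / 3.1 = 0.484 mg/kg, and 0.8 / 0.484 = 1.65.

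**The case against.** The strongest objection is that the point may be moot. The protocol calls the escalation completed, Part B was fully enrolled by May 2025, and every Part C group uses 0.4 mg/kg. The six-cohort list may be carried-over text. This stands as a limit: if 0.8 mg/kg will not be given, the rule has no practical effect. But Version 3.1 still lists the cohort and counts it in the planned sample size, so the question stays open.

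Second, the SRC reviews the data at exactly this point, and under Trial Procedures its review covers stopping criteria and dose adjustment. A committee seeing 2 of 3 severe related reactions would probably not carry on. That is a real safeguard, and the Cohort 1 rule is also only a referral to the SRC. Yet the Cohort 1 rule makes continuation an explicit question, whereas for later cohorts the text directs expansion and defines no stop at three.

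Third, the most plausible severe harm of this drug is thrombosis, which has its own stricter hold. This is correct and is why the table falls steeply with s. Non-thromboembolic reactions remain uncovered.

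Fourth, the monkey evidence is limited. The animals were healthy, the two tail cases had ulceration before dosing, and the mouse data gave a human equivalent dose of 8.13 mg/kg. These findings show why the rule might be needed at 0.8 mg/kg; they do not predict a rate.

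Finally, Figure 3-1 is not shown and may contain a branch for 2 of 3. The finding rests on the text alone.

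**Conclusion.** The point holds as a conditional, minor one. The text is not contradictory: the trigger simply lacks an upper limit. Followed literally, it doses three more patients after the terminate-or-reduce threshold has been met. That logic is exact and depends on no assumed rate.

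Its reach is one cohort and three patients, and only for non-thromboembolic reactions at 0.8 mg/kg. The chance runs from well under 1% to about 25%, depending on assumed rates and shares that the protocol does not supply. The more toxic the dose, the more often the superfluous expansion occurs. No endpoint, estimate or patient in Parts B and C is affected. It is worth considering because the correction costs almost nothing.

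**What to change.** On the Grade ≥3 leg, expand only when exactly 1 of the first 3 evaluable subjects is affected. If 2 or 3 are affected, enrol no one else at that dose and apply the terminate-or-reduce rule immediately through the SRC. State that this stop takes precedence over the Grade ≥2 leg, because two Grade ≥3 reactions also satisfy that leg's trigger of two and would otherwise bring the expansion back. The Grade ≥2 leg otherwise stays as it is. If Figure 3-1 shows the scheme differently, align it with the text. If 0.8 mg/kg will not be dosed, deleting that cohort from the plan is enough.

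The cost is one sentence. No patients are added, three fewer are exposed in the affected branch, the planned range of 16–33 stands, and the probability of termination is unchanged. The only loss is those three patients' data on whether to end the dose group or reduce the dose.

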This part is a randomized, open-label, multiple-dose efficacy-exploratory Phase IIb trial for prophylactic treatment. Three groups (A, B, C) will be selected, each enrolling 12 subjects, with the following dosing regimens:

Group A: Dose 0.4 mg/kg, Dosing frequency once every 4 weeks (Q4W)

Group B: Dose 0.4 mg/kg, Dosing frequency once every 6 weeks (Q6W)

Group C: Dose 0.4 mg/kg, Dosing frequency once every 8 weeks (Q8W)

Eligible patients will be randomized in a 1:1:1 ratio to Group A (0.4 mg/kg Q4W), Group B (0.4 mg/kg Q6W), or Group C (0.4 mg/kg Q8W), and will then enter a 6-month (24-week) treatment period. During the treatment period, Groups A, B, and C will receive 6, 4, and 3 doses, respectively. After the treatment period, subjects may enter an extension treatment period of up to 6 months (24 weeks). During the extension treatment period, Groups A, B, and C will receive up to 6, 4, and 3 additional doses, respectively. Efficacy endpoints will be collected at 28 days (Group A), 42 days (Group B), or 56 days (Group C) after the last dose, completing the final visit of the extension treatment period. The follow-up period extends to 84 days after the last dose. See Figure 3-3 for trial design details.

[figure not shown]

Figure 3-3: Schematic Diagram of Trial Design (Part C)

Sample Size

Part A: For the Hemophilia A/B indication, 6 dose cohorts are prespecified, with approximately 16–33 evaluable subjects planned. Cohort 1 will enroll 1–3 subjects, and each subsequent cohort will enroll 3–6 subjects.

Part B: Two dose groups are planned, with 12 subjects per group, for a total enrollment of 24 subjects, including patients with Hemophilia A/B and congenital coagulation Factor VII deficiency.

Part C: Three groups are planned, with 12 subjects per group, for a total enrollment of 36 subjects, including patients with Hemophilia A/B and congenital coagulation Factor VII deficiency.

Trial Duration

Part A: From screening of the first subject to the last visit of the last subject, the estimated trial duration is 11 months.

Part B: From screening of the first subject to the last visit of the last subject, the estimated trial duration is 15 months.

Part C: From screening of the first subject to the last visit of the last subject, the estimated trial duration is 21 months.

Subject Duration

Part A: For each subject from signing informed consent through completion of all protocol-specified visits, the expected maximum duration is approximately 115 days.

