※Note: Collected based on actual dosing duration. Added PD parameter: pro-inflammatory cytokines (IL-1beta, IL-6, TNF-alpha). If duplicate blood collection timepoints occur, collect only once

Collected blood samples will be centrifuged and stored frozen at –60°C or below. Test samples will be transported by a specialized cold chain logistics company to the central laboratory for analysis. Backup samples will be stored frozen at –60°C or below at the clinical trial institution or transported by a specialized cold chain logistics company to a sponsor-designated third party after trial completion.

Biological Sample Analysis:

All PK/PD biological samples collected from subjects will be transported to the central laboratory. Specific requirements will be executed according to the relevant standard operating procedures and testing requirements established by the central laboratory.

Safety and Immunogenicity Evaluation Parameters

Safety parameters: Incidence of AEs/SAEs/AESIs assessed through clinical signs and symptoms, vital signs, physical examination, laboratory tests (complete blood count, urinalysis, and blood biochemistry), coagulation function [PT, TT, INR, FIB, APTT, D-dimer], FDP, 12-lead ECG, injection site reactions, hypersensitivity/allergic reactions, thrombotic events, etc.; incidence of drug-related AEs/SAEs/AESIs; number and incidence of subjects with anti-drug antibodies (ADA) and neutralizing antibodies.

Immunogenicity parameters: Number and incidence of subjects with anti-drug antibodies (ADA) and neutralizing antibodies.

Efficacy Parameters (Part B)

Primary efficacy parameters:

At 12 weeks and 24 weeks of treatment, treatment-based annualized bleeding rate (ABR).

The ABR at 12 weeks of treatment can be calculated using the following formula: Total number of treated bleeding episodes from first dose to within 14 days after the 6th dose / $[(\text{date of 6th dose} - \text{date of first dose} + 14) / 365.25]$. The ABR at 24 weeks of treatment can be calculated using the following formula: Total number of treated bleeding episodes from first dose to within 14 days after the last dose / $[(\text{date of last dose} - \text{date of first dose} + 14) / 365.25]$.

Note: Total bleeding includes spontaneous and traumatic bleeding. A treated bleeding episode refers to a bleeding event for which factor replacement or bypassing agent therapy was administered.

Secondary efficacy parameters:

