1. At 12 weeks and 24 weeks of treatment, treatment-based annualized spontaneous bleeding rate;
2. At 12 weeks and 24 weeks of treatment, treatment-based annualized total joint bleeding rate (AJBR);
3. At 12 weeks and 24 weeks of treatment, treatment-based annualized menorrhagia bleeding rate (applicable only to female patients of childbearing age with menstruation who have congenital coagulation Factor VII deficiency);
4. At 12 weeks and 24 weeks of treatment, change from baseline in the Hemophilia Joint Health Score (HJHS) (Hemophilia A and B patients);
5. At 12 weeks and 24 weeks of treatment, change from baseline in the EuroQol-5 Dimension-5 Level (EQ-5D-5L) questionnaire.

Efficacy Parameters (Part C)

Primary efficacy parameters:

At 24 weeks of treatment and during the treatment period (including treatment and extension treatment periods), treatment-based annualized bleeding rate (ABR).

The following formulas can be used for calculation:

ABR at 24 weeks = (Number of treated bleeding episodes within the dosing interval after the last dose during the 24-week treatment period x 365.25) / (Date of last dose during the 24-week treatment period - Date of first dose + dosing interval)

ABR during the treatment period (including treatment period and extension treatment period) = (Number of treated bleeding episodes within the dosing interval after the last dose x 365.25) / (Date of last dose - Date of first dose + dosing interval)

Note: Total bleeding includes spontaneous and traumatic bleeding. A treated bleeding episode refers to a bleeding event for which factor replacement or bypassing agent therapy was administered.

The 'dosing interval' for the Q4W group is 28 days; for Q6W it is 42 days; for Q8W it is 56 days.

Secondary efficacy parameters:

1. At 24 weeks of treatment and during the treatment period (including treatment and extension treatment periods), treatment-based annualized spontaneous bleeding rate;
2. At 24 weeks of treatment and during the treatment period (including treatment and extension treatment periods), treatment-based annualized total joint bleeding rate (AJBR);
3. At 24 weeks of treatment and during the treatment period (including treatment and extension treatment periods), treatment-based annualized menorrhagia bleeding rate (applicable only to female patients of childbearing age with menstruation who have congenital coagulation Factor VII deficiency);

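### As written, the Part C primary ABR counts bleeds only in the last dosing interval but divides by the whole treatment period, so it is understated by a different factor in each group

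*Protocol*

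**What the plan says.** The protocol gives two formulas under Efficacy Parameters (Part C), Primary efficacy parameters.

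- ABR at 24 weeks: the numerator is "Number of treated bleeding episodes within the dosing interval after the last dose during the 24-week treatment period x 365.25" and the denominator is "Date of last dose during the 24-week treatment period - Date of first dose + dosing interval".
- ABR over treatment plus extension: the numerator is "Number of treated bleeding episodes within the dosing interval after the last dose x 365.25" and the denominator is "Date of last dose - Date of first dose + dosing interval".

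A note below them fixes the interval: "The 'dosing interval' for the Q4W group is 28 days; for Q6W it is 42 days; for Q8W it is 56 days".

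The corresponding 12-week formula under Efficacy Parameters (Part B) has the same kind of denominator, but its numerator is "Total number of treated bleeding episodes from first dose to within 14 days after the 6th dose". The Part B 24-week formula also starts its count at the first dose.

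**The concern.** An annualized rate needs events and time taken from the same window. In Part C the time runs from the first dose, while the events, as worded, come only from the interval after the last dose. Bleeds in all earlier intervals add follow-up time to the rate but no events.

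The size of the loss depends on the length of the dosing interval. All three groups receive 0.4 mg/kg, so the interval is the only thing that differs between the randomized regimens. Applied literally, the formula would understate bleeding everywhere and would also create a ranking in favour of the most frequent dosing. Part C would look better than Part B for the same reason, because the Part B formula is sound.

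**Working it through.** **Inputs.** Intervals are 28, 42 and 56 days (note under the Part C formulas). For the 24-week period, Trial Design states: "During the treatment period, Groups A, B, and C will receive 6, 4, and 3 doses, respectively". For the extension, "Groups A, B, and C will receive up to 6, 4, and 3 additional doses, respectively", which makes at most 12, 8 and 6 doses in total.

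**Denominator.** With *k* doses given on schedule at interval *τ*, it equals (k − 1) × τ + τ = k × τ.

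- Q4W: 5 × 28 + 28 = 168 days
- Q6W: 3 × 42 + 42 = 168 days
- Q8W: 2 × 56 + 56 = 168 days

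This reproduces the protocol's 24 weeks (24 × 7 = 168) exactly, so the denominator is the whole treatment period. With a full extension it is 12 × 28 = 8 × 42 = 6 × 56 = 336 days.

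**Numerator window as worded.** It is one interval, τ. In the 24-week period the last doses fall on D141, D127 and D113, and the window closes on D169 in each group.

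**Share of the denominator in which bleeds are counted.** This is τ / (k × τ) = 1/k. Under a constant bleeding rate, the reported ABR is the true ABR × 1/k.

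| | Q4W | Q6W | Q8W |
|---|---|---|---|
| 24 weeks: share counted | 28/168 = 1/6 | 42/168 = 1/4 | 56/168 = 1/3 |
| Reported if true ABR = 6 | 1.0 | 1.5 | 2.0 |
| Reported if true ABR = 12 | 2.0 | 3.0 | 4.0 |
| Full 48 weeks: share counted | 28/336 = 1/12 | 42/336 = 1/8 | 56/336 = 1/6 |
| Reported if true ABR = 6 | 0.5 | 0.75 | 1.0 |
| Reported if true ABR = 12 | 1.0 | 1.5 | 2.0 |

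The true rates are assumptions. Twelve per year corresponds to the hemophilia entry minimum of 3 treated bleeds in 3 months, and 6 is half of that. The shares do not depend on either value.

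**One cell in full (Q4W, 24 weeks, true ABR 12).** Expected bleeds over 168 days are 12 × 168 / 365.25 = 5.52. Expected bleeds in the last 28 days are 12 × 28 / 365.25 = 0.92. The formula gives 0.92 × 365.25 / 168 = 2.0.

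**False contrast at equal true rates.** Q8W to Q4W is (1/3) / (1/6) = 2.0, and Q6W to Q4W is (1/4) / (1/6) = 1.5. The same ratios hold at 48 weeks.

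**Partial extension.** The extension is stated as a maximum, so the understatement in the second formula lies between 6- and 12-fold for Q4W, 4- and 8-fold for Q6W, and 3- and 6-fold for Q8W.

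**Part B for comparison.** Its denominators are 5 × 14 + 14 = 84 days and 11 × 14 + 14 = 168 days. Its numerators span the same days, so the share is 1.

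**After correction.** If the Part C count starts at the first dose, the share is 1 in every group and a true ABR of 12 is returned as 12.0 in all three.

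**The case against.** The strongest reply is that the intended meaning can be recovered. The sentence introducing the formulas names the endpoint as the ABR at 24 weeks and over the treatment period including the extension, which points to the whole period. In Part B, the reference to days after a dose marks the end of the count. Trial Design likewise has Part C efficacy data collected up to 28, 42 or 56 days after the last dose. On that reading the interval is an end limit, and the start point was lost in drafting or translation. The formulas are also offered as ones that may be used, detailed methods are left to the SAP, and Part C is labelled exploratory, with no between-group test in the text shown.

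Much of this stands. An omission is the likeliest explanation, and the bias arises only if the formula is followed as written. The factors are not constants either. They assume a constant rate and on-schedule dosing, a subject who stops after one dose has matching windows (1/k = 1), and the 48-week figures are the full-extension maximum. Carrying the error over to the secondary bleeding rates is inference, since those have no formula of their own.

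This does not remove the defect. No sentence in the protocol gives the Part C count its start point, and no alternative formula is offered. Part B is introduced in equally permissive terms and is stated correctly. A SAP that counted from the first dose would contradict the protocol on its primary endpoint, and one that copied the protocol would give wrong results. An exploratory comparison of three regimens is still distorted by a bias tied to the regimen.

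**Conclusion.** The point holds for both Part C primary formulas: the numerator and denominator cover different windows. Taken literally, with a constant rate and on-schedule dosing, the 24-week ABR is understated 6-fold in Q4W, 4-fold in Q6W and 3-fold in Q8W, a loss of 83%, 75% and 67%. With a full extension the understatement is 12-, 8- and 6-fold. Equally effective regimens would show a spurious two-fold excess for Q8W over Q4W. The exact factors rest on those assumptions, but the mismatch of windows does not. Because it concerns the primary endpoint of the only randomized part, it should be corrected before any Part C analysis is programmed.

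**What to change.** Restate both numerators so that they cover the same days as their denominators:

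- 24-week ABR: the number of treated bleeding episodes from the first dose to one dosing interval after the last dose of the 24-week treatment period.
- ABR over treatment plus extension: the number of treated bleeding episodes from the first dose to one dosing interval after the last dose received.

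Keep the denominators and the × 365.25 factor as they are. Add one sentence stating that the annualized spontaneous, joint and menorrhagia rates use the same window, and carry the same wording into the SAP.

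The cost is a protocol clarification of two formulas plus that sentence. Bleeding events are already recorded throughout, so no new data, visits or subjects are needed.
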